In Parkinson's disease (PD), while motor disturbances are the predominant and most readily recognized symptoms, various non-motor symptoms frequently co-occur. Cognitive functions such as working memory and executive control are on average worse in PD, although with substantial variability across patients. This variability highlights the need for ongoing studies exploring the nature of cognitive deficits in PD and their relationship to disease severity and progression. This study utilizes pHMRI-measured dopamine buffering capacity in putative motor regions as a model of motor disease severity. We propose extending this approach to include measures of cognitive performance utilizing [the NIH Toolbox](#) [22]. The NIH Toolbox cognitive measures were chosen because they can be completed relatively quickly (important to minimize patient discomfort when assessed in the medication off state), because it incorporates tasks that directly assess functions known to be impaired in PD, and because of its recognized validity [23]. The hypothesis is that the extent of DA buffering capacity loss in pertinent regions (such as the caudate nucleus) will explain a significant fraction of the variance in specific cognitive abilities.

Secondary Aim

3. Test whether dopamine buffering capacity in caudate reflects severity of cognitive dysfunction.

STUDY DESIGN

Overall study timeline

The study is planned for complete enrollment within 3 years.

Overview of each subject's participation

After thorough clinical assessment on a screening visit, subjects return on a separate day for levodopa pHMRI. Clinical severity ratings are repeated. Regional CBF data from pre-specified brain VOIs (volumes of interest) are collected continually with ASL fMRI before levodopa, during a 10-minute i.v. loading dose, and then repeatedly over the next approximately 90 minutes.

Levodopa-naïve patients in Aim 2 will have all scan day procedures repeated identically on a second scan day after 6 ± 1 weeks of clinically dosed treatment with CD-LD.

Screening visit

1. Potential subjects will review a written informed consent document with the investigator or designee and will have opportunity to resolve questions or concerns. All procedures below are performed only after written documentation of consent.
2. We will collect the following measures at screening:
 - a. Basic demographic information
 - b. MRI safety checklist
 - c. Handedness (Edinburgh Handedness Inventory)

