Secondary analyses will correlate k_e 's from secondary VOIs to all measures of disease severity (off tapping speed, off UPDRS III, disease duration) and to cognitive test scores (NIH Toolbox task scores adjusted for age), using the off-period scores for measures done on the scan day. Voxelwise analyses will use SPM with an initial threshold of $t \geq 3.0$ and statistical inference at the cluster level with a false discovery rate of 0.05. Another secondary analysis will use the k_e computed from the button box tapping speeds from the more affected hand and the levodopa concentrations, independent of the perfusion MRI data ("tapping k_e "). We will test whether the tapping k_e correlates with the k_e from the midbrain or contralateral posterior putamen, or other VOIs.

Note that we expect that k_e for some VOIs will correlate better than for other VOIs with measures of disease severity or duration. This conclusion is based on the expectation that a specific clinical effect may be better associated with dopamine buffering capacity in a specific (set of) brain region(s).

Therefore we expect that the k_e -vs-clinical slope may differ significantly from zero only for a subset of the VOIs; in other words, we do not expect the slopes to be parallel across VOIs, and therefore will not include all VOIs in a single ANCOVA with a factor for VOIs. However, any errors in estimating pharmacokinetic parameters (i.e., in reconstructing the continuous function $C_p(t)$, plasma levodopa concentration as a function of time for $t \geq 0$) occur at the subject level. Such errors will affect all k_e estimates for that subject (i.e., across all VOIs). Therefore we cannot assume independence across VOIs, within subject, for the measured estimates of k_e .

Visual analog scale (VAS) measures of side effects will be analyzed as repeated measures ANOVAs. Other variables (demographics, clinical measures, NIH Toolbox scores, etc.) will be summarized or compared as appropriate using standard statistical methods.

Additional analysis details

We will examine interactions of the key analyses with subject demographics or disease variables such as age or presence of dyskinesias.

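### The plan expects k_e to track severity better in some VOIs than in others but specifies no test of that difference; separate tests against zero cannot supply one at n = 20

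*Combined protocol and SAP*

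**What the plan says.** In the combined protocol and SAP, the Data analysis part of the analysis plan makes a comparative prediction: "we expect that k_e for some VOIs will correlate better than for other VOIs with measures of disease severity or duration". It then recasts this as an expectation about significance, namely that the k_e-versus-clinical "slope may differ significantly from zero only for a subset of the VOIs". It adds that "we do not expect the slopes to be parallel across VOIs", and concludes that the analysis "will not include all VOIs in a single ANCOVA with a factor for VOIs". A caveat follows. Errors in reconstructing the plasma curve are shared by all of a subject's estimates, so "we cannot assume independence across VOIs, within subject, for the measured estimates of k_e". No method is attached to that caveat.

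Every k_e-versus-clinical analysis that is specified stays within one type of VOI or is voxelwise:
- Pearson correlations for midbrain.
- Repeated measures correlation across the two sides for posterior putamen.
- For the rest, "Secondary analyses will correlate k_e 's from secondary VOIs to all measures of disease severity", and also to cognitive scores.

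Under Additional analysis details, the planned interactions are with demographic and disease characteristics; VOI is not among them. That part also sets the 0.05 threshold, makes the correlation hypotheses one-sided and calls the secondary analyses exploratory.

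**The concern.** The premise does not lead to the conclusion. An ANCOVA with one common slope is indeed unsuitable if slopes differ by VOI. But whether slopes differ is the prediction itself, and a VOI-by-severity interaction is the term that tests it. The dependence within subject that the plan acknowledges calls for a comparison that uses the pairing. A set of separate correlations does not.

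The Secondary Hypothesis turns to particular regions for cognition: "the extent of DA buffering capacity loss in pertinent regions (such as the caudate nucleus) will explain a significant fraction" of the variance in specific abilities. As a test against zero that is fine. The difficulty arises with the comparative statement. Suppose k_e is significant in midbrain and not in caudate. The plan then contains no analysis that says whether the two correlations differ by more than sampling error. Equating a better correlation with significance in a subset of VOIs invites a conclusion that those results could not carry.

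**Working it through.** **Inputs from the documents.** n = 20 for Aim 1 (Sample size); alpha 0.05, one-sided (Additional analysis details); planning correlations r = 0.5 and r = 0.7 (Power considerations); ten named VOIs: midbrain, thalamus, and left and right posterior putamen, anterior putamen, caudate and accumbens. **Assumed:** the correlation of k_e between VOIs, which the documents do not give.

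**1. The plan's own figure.** Power is stated as above 80% at r = 0.5 and above 99% at r = 0.7. A one-sided noncentral t with 18 df and noncentrality √n·r/√(1−r²) gives:
- r = 0.5: √20 × 0.5/√0.75 = 2.58, power 79.9%.
- r = 0.7: √20 × 0.7/√0.51 = 4.38, power 99.5%.

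This is close to the stated figures. Simulation with both variables random gives 75.4% and 97.9%. All of these concern one VOI against zero. The plan gives no figure for a comparison between VOIs.

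**2. Discordance for one pair with equal true r.** The one-sided critical r at n = 20 is 0.378. If the two tests were independent, exactly one would be significant with probability 2p(1−p). At r = 0.5 this is 2 × 0.754 × 0.246 = 37%; at r = 0.7 it is 2 × 0.979 × 0.021 = 4%. Correlation between VOIs lowers it.

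**3. Simulation** (normal data; 60,000 studies per setting for pairs, 20,000 for ten VOIs; all VOIs share the same true r):

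| Inter-VOI correlation | Pair discordant, r = 0.5 | Of those, Williams test significant | Ten VOIs mixed, r = 0.5 | Ten VOIs mixed, r = 0.7 |
|---|---|---|---|---|
| 0.3 | 33% | 11% | not run | not run |
| 0.5 | 28% | 12% | 73% | 16% |
| 0.7 | 22% | 12% | 57% | 12% |
| 0.8 | 18% | 13% | 48% | 10% |
| 0.9 | 13% | 13% | 33% | 7% |

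Mixed means at least one VOI significant and at least one not.

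The same results can be indexed by the residual correlation q left after severity is removed. The total is r² + (1−r²)q. At r = 0.5, q = 0.2 gives 0.25 + 0.15 = 0.40, and q = 0.8 gives 0.25 + 0.60 = 0.85. Over q from 0.8 to 0.2:
- r = 0.5: a pair is discordant in about 16-31%, and ten VOIs are mixed in about 42-78%.
- r = 0.7: a pair is discordant in about 2-4%, and ten VOIs are mixed in about 7-14%.

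Simulation error moves these by about one point.

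**4. A direct test.** The Williams statistic for two correlations that share the clinical score is T = (r₁−r₂)·√{(n−1)(1+r₁₂) / [2((n−1)/(n−3))D + r̄²(1−r₁₂)³]} on n−3 df, where D = 1−r₁²−r₂²−r₁₂²+2r₁r₂r₁₂ and r̄ is the mean of r₁ and r₂. With both true correlations at 0.5, it rejects in 4.7-5.1% (two-sided 0.05).

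**5. Example.** Observed r = 0.45 gives one-sided p = 0.023, and r = 0.30 gives p = 0.099, so one is significant and the other is not. With r₁₂ = 0.5, D = 1 − 0.2025 − 0.09 − 0.25 + 0.135 = 0.5925 and T = 0.15 × √(28.5/1.342) = 0.69, p = 0.50. With r₁₂ = 0.8, T = 1.10, p = 0.29. Neither supports a difference.

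**6. Power of the direct test** (two-sided 0.05, n = 20) at inter-VOI correlation 0.3, 0.5, 0.7 and 0.8:
- true r of 0.5 vs 0.2: 21%, 29%, 45%, 64%.
- true r of 0.5 vs 0: 50%, 67%, 92%, 99.7%.

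**The case against.** The strongest reply has four parts.

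**The plan declines only a common-slope ANCOVA, and that is correct.** A reader might infer that it rejects the only kind of model that could test regional differences. The text does not support that. It does not discuss a version with an interaction, and it does not exclude tests of dependent correlations, a bootstrap or within-subject contrasts. These are omitted, not refused. Nor is shared plasma-curve error a second reason for the decision; it comes afterwards as a caveat. This stands, but the omission remains.

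**Regional specificity is not an aim.** Aim 1 and Aim 3 ask whether k_e in given regions reflects severity or cognition, which are questions against zero. A reader might infer that the authors will claim specificity from a pattern of significant and non-significant VOIs. The plan states no such rule, so that would be a prediction about a later report. This also stands. The weakness is that the plan's own wording treats the two ideas as the same and offers nothing else.

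**The size depends on the true correlation.** At r = 0.7 mixed patterns are uncommon, so it would be wrong to say that spurious patchiness is the usual result. The ten-VOI figure also simplifies: it sets left and right posterior putamen against one score, whereas the plan pairs each side with the contralateral score. The figure for one pair does not depend on that.

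**Slope comparisons have their own trap.** Regressing a within-subject difference in ln k_e on severity tests equal slopes, not equal correlations. At equal true r = 0.5, if the SDs of the two VOIs differ 1.5-fold (an assumption), it flags a difference in 11-25% of studies. This stands, and it determines the choice of method under the fix.

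**Conclusion.** The concern holds in a limited form. The plan makes a comparative prediction about VOIs, gives a reason against joint modelling that applies only to a common slope, and specifies no between-VOI comparison that uses the within-subject dependence it acknowledges. Separate tests against zero cannot support a regional difference. At the plan's own planning value of r = 0.5, equal regions look different on significance in about 16-31% of studies for one pair and about 42-78% for ten VOIs. A direct test errs in about 5%.

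These figures assume normal data, equal true correlations and a residual inter-VOI correlation of 0.8 to 0.2. At r = 0.7 the ten-VOI figure is about 7-14%. The two primary midbrain correlations do not depend on this point, and the secondary analyses are exploratory. It is therefore a change that should be made, not a flaw in the main result.

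**What to change.** Keep the per-VOI correlations. Replace the reasoning against a joint model with a direct comparison for a few named contrasts, each against the same clinical score: for example midbrain vs caudate, and posterior putamen vs caudate with side averaged.

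- **Preferred:** a Williams or Steiger test of dependent overlapping correlations, or a subject-level bootstrap of the difference in r. Report the difference with a 95% CI.
- **If slopes are compared instead:** a VOI-by-severity model with a subject effect and VOI-specific variances, or k_e standardised within VOI. Say which question is being answered, because equal correlations can go with unequal slopes.
- **Add a sentence:** significance in one VOI but not in another will not be taken as evidence of regional specificity.

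The cost is SAP wording and a short extra analysis of data already collected. The downside is modest power, about 21-64% for r = 0.5 vs 0.2 at inter-VOI correlation 0.3 to 0.8, so fewer specificity claims will be possible. A difference in r may also reflect how precisely k_e is estimated in each VOI, and the report should say so.

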- b. Tapping speed with the more affected hand (60 seconds sequentially depressing two keys 2cm apart with the index finger) using a device equivalent to an MRI-compatible button device.
- c. UPDRS part III
- d. Final blood sample
- e. Stop LD infusion
- f. VAS ratings
- g. Remove i.v. lines
- h. Record any benefit or side effect the patient noticed since the start of the infusion
- i. Provide a cab voucher if subject feels sleepy and had planned to drive home.

17. For Aim 2 subjects: Dispense supply of CD/LD tablets, confirm contact information, and confirm next study date.

Levodopa treatment between MR sessions (for subjects in Aim 2)

See “Treatments and Dosage,” a few pages below. This treatment is intended to match routine clinical practice. The initial treatment of PD varies among experts; CD/LD is a common option, and the most common one in the PI’s group practice, but other options include an MAO-A inhibitor, a dopamine agonist, or CD/LD combined with a COMT inhibitor. In other words, the 6-week initial treatment of Aim 2 subjects in this study is not off-label or experimental in the usual sense, but is standardized to a single treatment to reduce variability for the second pHMRI scan day.

With that exception, all procedures in this study are done for research purposes.

POTENTIAL RISKS

We have recently summarized the world literature on safety of i.v. levodopa and no SAEs are expected [16].

(The language below, in this section, is addressed to the patient, as in an informed consent document.)

You may experience one or more of the risks indicated below from being in this study. In addition to these, there may be other unknown risks, or risks that we did not anticipate, associated with being in this study. Some risks described in this consent document, if severe, may cause death. You will be told of any new information that may affect your willingness to participate in this study. [name] will answer any questions you have about these risks.

Levodopa

Likely:

- Temporary nausea
- Temporary sleepiness

Less likely:

- Temporary light-headedness (from lower blood pressure).
- Temporary vomiting
- Involuntary movements, hallucinations (seeing or hearing things that are not really there), delusions (being convinced of things that are objectively false), mental confusion, or impulse control disorders (like excessive gambling or change in sex drive). If any of these do occur, they are temporary.

Rare:

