If you are a woman capable of becoming pregnant, we will ask you to have a pregnancy test before beginning this study. You must use effective birth control methods and try not to become pregnant while participating in this study. If you become pregnant, there may be unknown risks to your unborn child, or risks to your unborn child that we did not anticipate. There may be long-term effects of the treatment being studied that could increase the risk of harm to an unborn child. You must tell the doctor if your birth control method fails while you are on the study. If you believe or know you have become pregnant while participating in this research study, please contact the research team member identified at the top of this document as soon as possible. Please discuss with the research team how long you need to wait before becoming pregnant after completing the treatment or procedures on this study.

If you are a sexually active male it is important that your partner not become pregnant during your participation in this study. There may be unknown risks to the unborn child or risks we did not anticipate. You and your partner must agree to use birth control if you want to take part in this study. If you believe or know that your partner has become pregnant during your participation in this study, please contact the research team member identified at the top of this document as soon as possible.

LOCATIONS / SITES OF STUDY

Data collection: Washington University School of Medicine

Data analysis: Washington University School of Medicine

STUDY DURATION

Anticipated duration of entire research activity per patient:

- Aim 2: Three days over the course of 1½ to 3 months*
- Patients not in Aim 2: Two days, which can occur up to a few weeks apart*

* One additional make-up scan day will be allowed for each subject, with his/her consent, in the event of technical problems that prevent completion of the scan day procedures. MRI equipment failure or a broken infusion pump are examples of such technical problems.

Anticipated duration of entire research activity:

Three years

SAMPLE SIZE

Aim 1: N = 20

Aim 2: N = 10 (up to 2 subjects can overlap between groups)

The N's above refer to subjects who are eligible after screening procedures and who continue in the study. Additional subjects may be screened to reach this number of eligible subjects.

Power considerations: For a first study of a method, there is no information available to confidently

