We will use a $p=.05$ threshold for significance tests. All the correlation hypotheses are one-sided, i.e. k_e will increase with increasing disease severity or duration (e.g., positive correlation for UPDRS scores or duration, as in Fig. 1 of the attached protocol; negative correlation for tapping speed). We will not correct for multiple comparisons among the 4 numbered primary analyses named above. The secondary analyses described above involve a number of comparisons but are exploratory. We will correct individual voxelwise analyses for multiple comparisons using SPM, as described above.

For the primary analyses (correlations of k_e and disease severity or duration), outliers will be determined at the level of the individual variables before computing the correlations. If the distribution of k_e values or of disease severity markers clearly deviates from a normal distribution on visual inspection because of outlying values, after transformation if appropriate, we will use a nonparametric analysis such as a Spearman correlation.

Subjects without “off” tapping score or UPDRS will be excluded from the pertinent analyses.

Subjects without a k_e value, due to missing perfusion MRI data or missing [LD] data, will be excluded from the primary analyses. However, subjects with a few missing [LD] data points that do not prevent a good fit to the PK model will be included; an example may be a subject with missing [LD] values only between (say) 30 and 90 minutes after the infusion starts.

SAFETY MONITORING

We have recently summarized the world literature on safety of *i.v.* levodopa and no SAEs are expected [16].

The Data Safety Monitoring Plan for this protocol will consist of the following measures:

- The PI will monitor for unanticipated problems, life-threatening events and deaths.
- We will report adverse events to the Washington University Human Research Protection Office (HRPO), and in annual reports to the sponsor and the FDA.

If any SAE occurs that is judged to be probably or definitely related to participation in the study, enrollment will stop until restarting is approved by the HRPO.

REFERENCES CITED

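### The pause after a related SAE stops enrollment only; as written it does not hold research levodopa infusions still due in subjects already enrolled

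*Combined protocol and SAP*

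**What the plan says.** The data safety monitoring plan (Safety Monitoring) has two listed measures: monitoring by the PI, and reporting of adverse events to the HRPO and in annual reports to the sponsor and the FDA. One action rule follows. Its trigger is "If any SAE occurs that is judged to be probably or definitely related to participation in the study", and its consequence is that "enrollment will stop until restarting is approved by the HRPO".

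The infusion schedule is set out elsewhere:

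- **Screening and first scan.** Under Study Design, consent and eligibility review take place at screening, and the levodopa scan is on a separate day. For subjects outside Aim 2, Study Duration gives "Two days, which can occur up to a few weeks apart".
- **Second scan.** Aim 2 subjects have "all scan day procedures repeated identically on a second scan day", after 6 ± 1 weeks of oral carbidopa-levodopa. Study Duration gives their participation as "Three days over the course of 1½ to 3 months".
- **Make-up scan.** "One additional make-up scan day will be allowed for each subject", with consent, if technical problems prevent completion of a scan day.
- **Who is counted.** Sample Size defines the N's as "subjects who are eligible after screening procedures and who continue in the study".
- **Status of the infusion.** After describing the Aim 2 oral treatment as routine clinical practice, the section on levodopa treatment between MR sessions adds: "With that exception, all procedures in this study are done for research purposes".

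**The concern.** A pause after a related SAE should keep other subjects from the same research exposure until someone has reviewed the event. Here the exposure of interest is an intravenous levodopa infusion given under an IND, and it comes after the visit at which a subject consents and is found eligible. A rule that halts only enrollment therefore acts upstream of the exposure. Subjects between screening and their last scan are the ones closest to an infusion, and the rule as written does not cover them.

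The infusion is a research procedure, so postponing it withholds no clinical care. The protocol also states that it expects no SAEs. A related one would contradict that premise, and that is when further research exposure should wait for review.

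**Working it through.** The plan gives no figure on this point to reproduce. The check compares the rule with the visit schedule, and then sizes the part that can be counted.

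**1. What the rule halts.** The only thing the sentence stops is enrollment, so the restart that needs HRPO approval is most naturally the restart of enrollment. Nothing else in the text available for review suspends scan days or infusions. Part of the patient-facing risk text was not available, but the Safety Monitoring section was complete.

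**2. Where the infusions sit.** Inputs from Sample Size: Aim 1 N = 20, Aim 2 N = 10, planned overlap up to 2. Aim 1 subjects have one infusion and Aim 2 subjects have two. Before make-up days:

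- no overlap: 20 × 1 + 10 × 2 = 40 infusions in 30 subjects;
- overlap of 2: 18 × 1 + 10 × 2 = 38 infusions in 28 subjects.

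All of them follow the screening visit. Ten are Aim 2 second infusions.

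**3. Why an enrollment stop misses the second infusions.** The shortest gap between Aim 2 scans is 6 − 1 = 5 weeks. Any second infusion due within a review of up to 5 weeks therefore belongs to a subject who had the first scan before the pause began. Stopping enrollment cannot prevent it.

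**4. How often one would fall in the review period.** Inputs: 10 second infusions, and 3 years = 156 weeks of research activity (Study Duration). Assumptions not in the documents: second infusions spread evenly over that time, and a review lasting w = 1, 2 or 4 weeks. The expected number is 10w/156, and the chance of at least one is 1 − exp(−10w/156). The check column treats the dates as 10 independent uniform draws.

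| Review (weeks) | Expected number, 10w/156 | 1 − exp(−10w/156) | Check: 1 − (1 − w/156)^10 |
|---|---|---|---|
| 1 | 0.064 | 6.2% | 6.2% |
| 2 | 0.128 | 12.0% | 12.1% |
| 4 | 0.256 | 22.6% | 22.9% |

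Each probability is conditional on a related SAE having occurred. First scans pending after screening and make-up scans would add to it and are not counted.

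**5. After enrollment closes.** If enrollment ends at screening and the last subject enrolled is in Aim 2, both of that subject's infusions come after enrollment is complete, within a participation of 1½ to 3 months. During that time the rule has nothing to stop.

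**The case against.** **The meaning of enrollment.** The protocol does not define the word. Study Design plans complete enrollment within 3 years, and Study Duration gives three years for the whole research activity, so the term may be used loosely. If a subject counts as enrolled only on continuing to the scan, the rule might already stop pending first scans. This stands as an ambiguity, and it makes first scans and the last-subject scenario less certain. It does not reach Aim 2 second scans or make-up days, because a repeat scan in an existing subject is not enrollment in any ordinary sense.

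**Existing oversight.** The data are collected at one institution under a sponsor-investigator. The PI monitors for unanticipated problems and is told of health changes before each scan, and the HRPO is involved once restarting needs its approval. Either could stop scans, and nothing obliges scans to proceed. That is true, but the hold is then discretionary for enrolled subjects while it is automatic for people not yet enrolled.

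**Size.** The percentages rest on assumed accrual and review length, and the trigger is unlikely. The infusion totals 68 mg levodopa over 2.5 hours for a 60-year-old, 70 kg subject, and the protocol reports earlier use of the method. If the SAE occurs in an Aim 2 subject before that subject's second scan, only 9 other second infusions are relevant. Then 1 − (1 − w/156)^9 gives 5.6%, 11.0% and 20.8%. The correction is fair and small.

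**The remedy.** A blanket hold would also apply when the SAE had nothing to do with the infusion, and would then depend on the HRPO to release scans. That is so, but it makes holding the default and release the decision.

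**Conclusion.** The concern holds as a gap in the written rule. The firm core is the 10 Aim 2 second infusions and any make-up days. On the ordinary reading of enrollment, first scans pending after screening are also uncovered.

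Given a related SAE, the chance that at least one Aim 2 second infusion falls inside a 1-, 2- or 4-week review is about 6%, 12% or 23% (slightly lower if only 9 are relevant). These figures are illustrative, since they assume an even spread of infusions and those review lengths. The documents give no SAE rate from which to derive an unconditional risk; it is much smaller. The sponsor should make the change because it corrects the scope of a safety rule already adopted, at very little cost.

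**What to change.** Amend the action sentence in Safety Monitoring along these lines:

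> After an SAE judged probably or definitely related to study participation, enrollment and every remaining research infusion or scan day in subjects already enrolled are on hold until the HRPO approves resumption.

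Add two clarifications. Oral carbidopa-levodopa in Aim 2 is continued or stopped for each subject by the PI's clinical judgement. If the SAE arose from something other than the infusion day, the HRPO may release scans early.

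The cost is a one-sentence protocol amendment plus these clarifications. If a pause ever occurs, an Aim 2 second scan may fall outside its 6 ± 1 week window; each such scan affects 1 of the 10 Aim 2 subjects.
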